6.2.4.2. Relationship to Investigational Product

The investigator must assign a relationship of each AE to the receipt of the investigational product. The investigator will use clinical judgment in conjunction with the assessment of a

plausible biologic mechanism, a temporal relationship between the onset of the event in relation to receipt of the investigational product, and identification of possible alternate etiologies including underlying disease, concurrent illness or concomitant medications. The following guidelines should be used by the investigator to assess the relationship of an AE to study product administration. **ONLY A PHYSICIAN CAN MAKE THIS DETERMINATION.**

Not related: Relationship to investigational product. Applies to those events for which evidence exists that there is an alternate etiology.

Unlikely: Likely unrelated to the investigational product. Likely to be related to factors other than investigational product, but cannot be ruled out with certainty.

Possible: An association between the event and the administration of investigational product cannot be ruled out. There is a reasonable temporal association, but there may also be an alternative etiology such as the subject's clinical status or underlying factors including other therapy.

Probable: There is a high degree of certainty that a relationship to the investigational product exists. There is a reasonable temporal association, and the event cannot be explained by known characteristics of the subject's clinical state or factors including other therapy.

Definite: An association exists between the receipt of investigational product and the event. An association to other factors has been ruled out.

6.2.4.3. Severity Assessment

All AEs will be assessed for severity by the investigator. Inherent in this assessment is the medical and clinical consideration of all information surrounding the event including any medical intervention required. Each event will be assigned one of the following categories: mild, moderate, severe, or life-threatening.

Table 4: Severity Assessment Scale

Category	Grade	Description
Mild	1	Mild symptoms; clinical or diagnostic observation only. (Does not interfere with routine activities, minimal discomfort)
Moderate	2	Interferes with routine activities Moderate level of discomfort
Severe	3	Severe or medically significant but not immediately life-threatening; hospitalization indicated; Unable to perform routine activities; Significant level of discomfort
Life-threatening	4	Urgent intervention indicated (Hospitalization or ER visit for potentially life-threatening event)
Death	5	Death related to AE

The severity assessment criteria may be used for any symptom not included in the grading scale. Any grade 4 (life-threatening) AE must be reported as an SAE. The eCRF for AEs will reflect

only the highest severity for continuous days an event occurred. The criteria in **Table 4** will be followed; however, if a subject is evaluated in an emergency room setting for nonlife threatening illness or symptoms (i.e., visits emergency department on weekend for mild problems because the physician's office is closed), the information from that visit will be reviewed and severity of the AE will be assessed according to the subject's clinical signs and symptoms.

As defined by the ICH guideline for GCP, the term "severe" is often used to describe intensity (severity) of a specific event (as in mild, moderate, or severe myocardial infarction); the event itself however, may be of relatively minor medical significance (such as severe headache). This is **not** the same as "serious", which is based on subject/event **outcome or action** criteria usually associated with events that pose a threat to a subject's life or functioning. Seriousness (not severity) serves as a guide for defining regulatory reporting obligations.

6.2.4.4. Recording Adverse Events

Methods/Timing for Assessing, Recording and Analyzing Safety Measurements (Endpoints)

AEs and SAEs will be assessed at each study visit and documented in the source records. All AEs will be recorded on the eCRFs using accepted medical terms and/or the diagnoses that accurately characterizes the event. SAEs will be documented using the SAE paper form. It should be noted that the form for collection of SAE information is not the same as the AE eCRF. Where the same data are collected on both forms, the forms must be completed in a consistent manner. For example, the same event term should be used on both forms.

When a diagnosis is known, the AE term recorded on the eCRF will be the diagnosis rather than a constellation of symptoms. The investigator will assess and record for all AEs/SAEs: a description of the event (if the event consists of a cluster of signs and symptoms, a diagnosis should be recorded rather than each sign and symptom): onset date and time, and resolution date and time: intensity (recorded as mild, moderate or severe): relationship to study drug (recorded as unrelated, unlikely related, possibly related, probably related and definitely related): outcome (recorded as recovered, recovering, resolved with sequelae, not resolved, fatal, ongoing (end of study) or unknown if applicable): action taken with the study product (recorded as no action taken, dose reduced, interrupted, discontinued). When an event has not resolved by study closure, it will be documented on the AE eCRF as "ongoing."

The timeframe for the collection of AEs and SAEs for each subject begins at the first administration of investigational product (Visit 3, Day 0) through Visit 4, Day 4.

Duration of Follow-Up of Subjects after Adverse Events

Investigators are required to follow SAEs to resolution, even if this extends beyond the prescribed reporting period. Resolution is the return to baseline status or stabilization of the condition with the probability that it will become chronic. The SAE outcomes will be reported to the sponsor's representative using the Serious Adverse Event Report Form.

Investigators are not obligated to actively seek SAEs in former subjects; however, if an SAE, considered to be related to the investigational product is brought to the attention of the investigator *at any time* following completion of the study, the event will be reported to the

sponsor's safety office (see below). Other extensive reporting requirements are given in the study protocol.

6.2.4.5. AE-related Withdrawal of Consent

Any AE-related withdrawal of consent during the study must be reported *immediately (within 72 hours of identification)* by email or fax to the sponsor's representative. Report the withdrawal to US Investigational Review Board (IRB of Record) and/or the USAMRMC ORP in accordance with IRB policy.

6.2.4.6. Pregnancy

Each pregnancy must be reported **within 72 hours of identification** by completing and submitting the Sponsor approved Pregnancy Report Form (paper) via email or fax to the sponsor's safety office (CSSD, Product Safety Surveillance Branch). Report the incident to US Investigational Review Board and/or the USAMRMC ORP in accordance with IRB policy.

Subjects who become pregnant after Day 0 will be followed to term, and the following information will be gathered, documented, and reported on the follow-up Pregnancy Report Form for outcome, date and type of delivery, Apgar scores, health status of the mother and child including the child's gender, height and weight. Complications and or abnormalities should be reported including any premature terminations. A pregnancy is reported as an AE or SAE only when there is suspicion that the investigational product may have interfered with the effectiveness of contraception or there was a serious complication in the pregnancy including a spontaneous abortion or an elective termination for medical rationale.

The decision on whether to remove the participant from the study will be made by the investigator and the participant following consultation with the Sponsor.

6.3. Proof of Concept Evaluations (Secondary Analysis)

6.3.1. Quigley Hein-Turesky Plaque Index (QHT) Whole Mouth Score

The mouth generally contains 28 teeth arranged in four quadrants, 7 teeth per quadrant (maxillary-buccal, maxillary-lingual, mandibular-buccal, mandibular-lingual). Each tooth has 6 surfaces for plaque evaluation so that a mouth with all teeth and surfaces present has $4 \times 7 \times 6 = 168$ surfaces. For each evaluable surface the evaluator assigns a numerical score from 0 to 5 relative to the plaque present, with 0 meaning no plaque, and 5 the worst or highest plaque determination. Criteria for each score is given in [\[Tureskey-1970\]](#).

Some of the 168 possible surfaces may not be evaluable due to either the particular tooth is missing or due to other dental issues as determined by the evaluator.

The whole mouth QHT score at a given dental appointment is the sum all scores divided by the number of evaluable surfaces. In other words, the QHT is the arithmetic average of all scores from the evaluable surfaces, so that scores for surfaces not evaluable are not imputed.

The QHT evaluations for each subject are planned to occur at Screening (Visit 1), Day 0 (Visit 3), and Day 4 (Visit 4).

6.3.1.1. Valid QHT Whole Mouth Score

A subject must have at least 20 teeth with all 6 surfaces evaluable in order for the QHT whole mouth score to be used in this study. Subjects who do not satisfy this criterion at the baseline evaluation will be excused from the study. Generally this determination will be made at the screening visit, and most likely a subject qualifying at screening will also qualify at baseline.

6.3.1.2. QHT Quadrant Scores

The arithmetic average of the scores obtained from each of the 4 quadrants (maxillary-buccal, maxillary-lingual, mandibular-buccal, mandibular-lingual) will be assessed again using only the evaluable surfaces from each quadrant. No additional restriction on the number of evaluable surfaces from each quadrant will be made.

6.3.1.3. QHT Tooth Surface Scores

A set of up to 168 individual surface scores will be obtained at each of the QHT evaluations for each subject and will be part of the data set for the study.

7. Statistical Methods for Data Analysis

7.1. Primary (Safety) Analyses

7.1.1. Adverse Events

A subject listing of deaths, other serious AEs, and discontinuations due to adverse events will be presented in tabular form by treatment received. Information will include a description of the event, the study day when the event was first observed, severity if applicable, relationship to study drug, resolution status of the event, subject status within the study (if applicable).

Summaries of adverse events by SOC only, and by event severity will be given by study arm. Separate tabular summaries by study arm, system organ class (SOC) and by preferred term (PT) within SOC will be given for:

- All AEs
- AEs possibly, probably, definitely related to study medication.

For each SOC and SOC, PT combination the estimated incidence proportions and estimated incidence rates will be given by treatment received.

The incidence proportion will be calculated as the number of subjects with a given treatment (KSL-W, placebo) having at least one AE with that SOC or SOC-PT classification, divided by the number of subjects with that treatment (expressed as a percent).

The incidence rate will be calculated as the number of adverse events with that SOC or SOC-PT classification divided by the total study exposure from all subjects with a given treatment. The study exposure is determined in days (see 3.1.2), but the total study exposure will be converted to subject-weeks. The total number of events and the rate in events per subject-week will be given. Since incidence rate takes into account exposure, this may be the measure more applicable to combine with other studies.

Subject listings of adverse events will include the verbatim AE terms as well as the SOC, PT. Severity, relationship with study drug, resolution of the event, and ongoing status of the subject within the study will also be shown in the subject listings, which will be presented by treatment and subject within treatment.

Adverse event data collected on paper forms will be described in the final Clinical Study Report and not displayed in a table or listing. This will include any additional maternal or paternal adverse events which will be collected on the Pregnancy Surveillance Form as well as any data collected on the Serious Adverse Event Form.

7.1.2. Vital Signs

Descriptive summaries will be provided by treatment for systolic, diastolic BP, heart rate, temperature, and respiration, at screen, Day 0, and Day 4. Change from baseline will be computed as the Day 4 assessment minus the Day 0 assessment. For each variable at each visit, and change from baseline the sample mean, standard deviation, minimum, maximum, 25th percentile, median, and 75th percentile will be provided.

7.1.3. Physical Exam and Urine Pregnancy Test

The percent of subjects by treatment with “relevant physical exam findings” will be presented for the screening and Day 4 visits. The description of the relevant findings will be found in the physical exam subject listing, classified by treatment, subject, and visit. If very few relevant findings are discovered they will be listed on the summary table.

The number and percent of women of child-bearing age will be summarized at the screening and Day 4 visits by treatment received. The number of such women taking the urine pregnancy test, and the findings of the test (positive or negative) will be summarized again by visit and treatment.

7.2. Plaque Re-growth: Secondary Proof of Concept Analyses

7.2.1. Whole Mouth QHT Score

An analysis of covariance (ANCOVA) model will be fit to the subjects’ change in plaque re-growth from baseline in the QHT score (baseline minus Day 4) for subjects in the FAS population.

Primary POC model: The primary model will include randomized study arm (KSL-W, placebo) and the baseline QHT score.

Least squares means and standard errors will be summarized for KSL-W, placebo, and the KSL-W minus placebo mean difference. A 95% confidence bound will be presented for the mean difference along with a 2-tailed p value testing the null hypothesis that the mean difference in the mean change in plaque re-growth is zero. The estimated common error variance together with a 95% (equal tailed) confidence bound will be presented.

The model assumptions include the following:

- Baseline minus Day 4 subject QHT differences have a normal distribution, conditioned on the baseline observation.

- The relationship between the mean difference and baseline is linear, with slope not dependent on study arm.
- The model error variance does not depend on study arm or the mean difference.
- The QHT evaluator has no effect on the mean difference, error variance, or baseline slope.

Each of these model assumptions will be checked, and the findings of these determinations will be summarized along with the above information. Violations of the model assumptions affecting later decisions based on this information will be investigated, particularly their impact on the conclusions of the study.

Secondary Investigations: A secondary investigation involving a full model including study arm, baseline QHT score, QHT evaluator and all possible 2-factor interactions will be conducted.

Results of the primary model applied to the per-protocol (PP) population whole-mouth QHT scores will be summarized as with the FAS population, as well as the primary and secondary model parameter estimates for the PP population.

This study was not powered for a specific expected effect size, hence all p values are descriptive and no adjustment will be made for multiple p values.

The results of the primary and secondary investigations will be summarized in a Statistical Analysis Report (SAR), including the model assumptions investigations and estimates, standard errors of the primary and secondary model parameters.

7.2.2. QHT Score by Mouth Quadrant

Least squares means and standard errors will be summarized for KSL-W, placebo, and the KSL-W minus placebo mean difference for each of the 4 mouth quadrants using the primary model. Also, 95% confidence bounds will be presented for the mean difference by quadrant, along with a 2-tailed p value for the null hypothesis that the mean difference in the mean change in plaque re-growth for that quadrant is zero. This summary will be generated for both the FAS and PP populations.

The FAS population, the study arms are being compared regardless of the treatment actually received, while for the PP population the results are compared based on the actual treatment received. It is expected that treatment actually received will very likely correspond to the study arm assignment.

7.2.3. Descriptive Summary of QHT Scores

The mean, standard deviation, minimum, median, and maximum will be summarized by study arm (treatment) and by visit (baseline, Day 4) for the whole-mouth QHT scores and for each of the 4 mouth quadrant QHT scores. These summaries will be generated for the FAS and PP populations.

Individual surface summary distributions will be presented by visit and study arm to allow spot comparisons of the change in score from baseline to day 4 by treatment.

7.3. Intra-oral Exam: Hard and Soft Tissue

Summaries of the number and percent present for each of 5 hard tissue issues will be summarized by study arm and visit (Screen, Day 0, and Day 4) for the Safety, FAS, and PP populations. A similar summary will be generated for the 14 soft tissue issues. Listings will also be prepared by subject.

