Title of Study: A Double-Blind, Randomized, Placebo Controlled, Clinical Trial of an Antiplaque Chewing Gum (30 mg) - Phase 2 Proof of Concept in a Generally Healthy Patient Population	
Study Center: Salus Research [name]	
Principal Investigator: [name], MPA	
Sub-Investigator: [name], RDH, BSEd, MS (Examiner)	
Study Period (years): Estimated date first subject enrolled: August 2016 Estimated date last subject completed: August 2016	Phase of development: 2
Objectives: Primary: 
• To assess the safety and tolerability of KSL-W (30 mg dose) delivered in a chewing gum formulation compared to a placebo gum formulation Secondary: 
• To assess the proof of concept change in plaque regrowth from baseline in the Quigley Hein-Turesky Plaque Index (QHT) of KSL-W (30 mg dose) compared to a placebo gum formulation• To evaluate the proof of concept of KSL-W (30 mg) in change in plaque regrowth based on sub-scores from specific regions of the upper jaw, lower jaw, buccal and lingual surface based on the QHT	
Methodology: This study is a Phase 2 two-armed placebo-controlled, double-blind, randomized (1:1) multiple dose, single center study to evaluate the safety and proof of concept of 30 mg KSL-W administered in a chewing gum formulation 3 times per day over 4 treatment days. Oral hygiene (teeth brushing, flossing and/or mouth wash rinse) is prohibited throughout the trial beginning 12 to 16 hours before both the screening and Baseline (Day 0) visits, during the 4 days of treatment (Days 0, 1, 2, and 3) and ending after the periodontal examination and plaque assessment on Day 4. The ability of KSL-W to reduce existing supragingival plaque will be assessed. The oral soft (OST) and oral hard tissues (OHT) will be examined. Changes from baseline, such as soft tissue erythema, ulceration and sloughing, will be noted.	
Estimated Number of Subjects Screened: 35	
Estimated Number of Subjects Enrolled: 26	

Number of Subjects (planned): 24

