6.2.3. Intraoral Examination

6.2.3.1. Oral Soft Tissue Examination

The OST examination will be performed by visually inspecting the oral cavity and perioral area using a dental light, dental mirror, periodontal probe and gauze. Any abnormalities at baseline will be recorded in order to detect changes such as the development of erythema, ulceration, or tissue sloughing should they occur during the four day study period.

The structures examined will include the labial mucosa (including lips), buccal mucosa, mucogingival folds, gingival mucosa, hard palate, soft palate, tonsillar area, pharyngeal area, tongue, sublingual area, submandibular area, salivary glands, temporomandibular joint, and any other area as deemed necessary by the investigator. The same examiner will conduct the subject's OST during the study.

OST observations will be listed as "Normal" or "Abnormal." Abnormal observations will be documented and described in the subject's study records. Any changes will be recorded, severity assessed according to standard dental examination procedures, and a decision made with respect to whether or not these changes are related to treatment with the study drug. New or worsened OST findings occurring after the first use of the study product will be recorded as AEs.

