Enamel Irregularities	n (%)	n	n (%)	n	n
Tooth Fracture	n (%)	n	n (%)	n	n
Gross Decay	n (%)	n	n (%)	n	n
Implants	n (%)	n	n (%)	n	n
Faulty Restorations	n (%)	n	n (%)	n	n

n = number with condition Present, (%) = 100 n/N, with N = total for study arm

Subject listing of Oral Hard Tissue: LREF10

(TREF16.2 FAS, TREF16.3 Per-protocol population)

OHTE pgs 11 (screen), 32 (Day 0), 80 (Day 4) eCRF

TREF17.2

Intra-oral Exam by Visit

Oral Hard Tissue

Safety Population: KSL-W (N=xx), Placebo (N=xx)

Day 0	KSL-W		Placebo	
	N=xx		N=xx	
	Present	Absent	Present	Absent
Enamel Irregularities	n (%)	n	n (%)	n
Tooth Fracture	n (%)	n	n (%)	n
Gross Decay	n (%)	n	n (%)	n
Implants	n (%)	n	n (%)	n
Faulty Restorations	n (%)	n	n (%)	n

n = number with condition Present, (%) = 100 n/N, with N = total for study arm

Subject listing of Oral Hard: LREF10

(TREF16.2 FAS, TREF16.3 Per-protocol population)

OHTE pgs 11 (screen), 32 (Day 0), 80 (Day 4) eCRF

TREF16.1

Intra-oral Exam by Visit

Oral Hard Tissue

Safety Population: KSL-W (N=xx), Placebo (N=xx)

		KSL-W		Placebo	
		N=xx		N=xx	
Day 4		Present	Absent	Present	Absent
		n (%)	n	n (%)	n
Enamel Irregularities					
Tooth Fracture		n (%)	n	n (%)	n
Gross Decay		n (%)	n	n (%)	n
Implants		n (%)	n	n (%)	n
Faulty Restorations		n (%)	n	n (%)	n

n = number with condition Present, (%) = 100 n/N, with N = total for study arm

Subject listing of Intra-oral Exam: LREF09

(TREF16.2 FAS, TREF16.3 Per-protocol population)

OHTE pgs 11 (screen), 32 (Day 0), 80 (Day 4) eCRF

TREF17.1

Intra-oral Exam by Visit

Oral Soft Tissue

Safety Population: KSL-W (N=xx), Placebo (N=xx)

Screen	KSL-W		Placebo	
	N=xx	N=xx	Present	Absent
Gingival Mucosa	n (%)	n (%)	n (%)	n (%)
Labial Mucosa (Including Lips)	n (%)	n (%)	n (%)	n (%)
Buccal Mucosa	n (%)	n (%)	n (%)	n (%)
Mucogingival Folds	n (%)	n (%)	n (%)	n (%)
Hard Palate	n (%)	n (%)	n (%)	n (%)
Soft Palate	n (%)	n (%)	n (%)	n (%)
Tonsillar Area	n (%)	n (%)	n (%)	n (%)
Pharyngeal Area	n (%)	n (%)	n (%)	n (%)
Sublingual Area	n (%)	n (%)	n (%)	n (%)
Submandibular Area	n (%)	n (%)	n (%)	n (%)
Salivary Glands	n (%)	n (%)	n (%)	n (%)
Tongue	n (%)	n (%)	n (%)	n (%)
TMJ	n (%)	n (%)	n (%)	n (%)
Other	n (%)	n (%)	n (%)	n (%)

n = number with condition Present, (%) = 100 n/N, with N = total for study arm

Subject listing of Intra-oral Exam: LREF09

(TREF17.2 FAS, TREF17.3 Per-protocol population)

OSTE pgs 12 (screen), 33 (Day 0), 78 (Day 4) eCRF

TREF17.1

Intra-oral Exam by Visit

Oral Soft Tissue

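### The intra-oral exam tables give counts visit by visit and show no within-subject change from Day 0 to Day 4, so new soft-tissue findings can be offset in them by resolutions

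*SAP*

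**What the plan says.** SAP 7.3 sets the hard-tissue summary as "Summaries of the number and percent present for each of 5 hard tissue issues will be summarized by study arm and visit". It then adds "A similar summary will be generated for the 14 soft tissue issues" and "Listings will also be prepared by subject". The footnote to the TREF17 shells in SAP 11.2 defines the entries: "n = number with condition Present, (%) = 100 n/N, with N = total for study arm". Screen, Day 0 and Day 4 are laid out as separate tables. None has a column for change, shift or new onset.

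The purpose of the baseline exam is given in SAP 6.2.3.1: "Any abnormalities at baseline will be recorded in order to detect changes such as the development of erythema, ulceration, or tissue sloughing". The Protocol synopsis (Methodology) says the same of the study as a whole: "Changes from baseline, such as soft tissue erythema, ulceration and sloughing, will be noted". The Day 0 exam comes before the first chew (Protocol 9.1.2), so it is a true pre-treatment baseline.

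SAP 6.2.3.1 also provides a second route for soft tissue: "New or worsened OST findings occurring after the first use of the study product will be recorded as AEs". SAP 6.2.3.2 on hard tissue has no matching sentence. It asks only for an absent or present entry and a description of anything present.

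**The concern.** Safety and tolerability is the primary objective, and local oral mucosal reactions come first among the safety criteria in the synopsis. The intra-oral exam is the systematic measure of them: a fixed list of sites, examined in every subject before and after treatment. What one would compare between arms is how many subjects had a finding on Day 4 that was not there on Day 0. Separate visit totals do not give that number. The SAP tabulates within-subject change for vital signs (SAP 7.1.2, Day 4 minus Day 0) but plans no paired summary for the exam that bears most directly on local tolerability.

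**Working it through.** The documents give no figure for this point, so there is none to reproduce. The check asks what two visit totals can reveal about new findings.

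**Inputs**
- n = 13 per arm (Protocol 5.7).
- k0 and k4 are the numbers abnormal at one site on Day 0 and Day 4. The documents give no expected rates, so all values below are assumed for illustration. Every subject is taken to be examined on both days.

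**Formula.** Let *a* be the new findings, *r* the resolved ones and *p* those abnormal on both days. Then k0 = p + r and k4 = p + a, so a − r = k4 − k0. The table fixes only the difference between new and resolved. Hence

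max(0, k4 − k0) ≤ a ≤ min(k4, n − k0),

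and the number at risk of a new finding is n − k0.

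**Results**

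| Day 0 | Day 4 | New cases possible | At risk | New, % of at risk |
|---|---|---|---|---|
| 0/13 (0.0%) | 2/13 (15.4%) | exactly 2 | 13 | 15.4 |
| 2/13 (15.4%) | 2/13 (15.4%) | 0 to 2 | 11 | 0.0 to 18.2 |
| 4/13 (30.8%) | 3/13 (23.1%) | 0 to 3 | 9 | 0.0 to 33.3 |
| 3/13 (23.1%) | 5/13 (38.5%) | 2 to 5 | 10 | 20.0 to 50.0 |

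The second row looks like no change and the third like an improvement, yet each allows new findings. The first row shows the limit of the problem: if nobody is abnormal at a site on Day 0, the Day 4 count is the number of new cases.

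**Worsening.** Soft-tissue items are recorded as normal or abnormal, with free text for abnormal ones. A subject abnormal on both days who got worse stays in the same category. A shift table built on this field would not show the worsening either, so it has to come from the AE record, which carries severity.

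**Hard tissue.** The five items are enamel irregularities, tooth fracture, gross decay, implants and faulty restorations. These hardly resolve in four days, and inclusion criterion I09 has subjects forgo optional dental work. With r = 0 the formula reduces to a = k4 − k0, and nothing is masked. The hard-tissue gap is the missing AE rule: only the general AE definition, and the treatment-emergent wording that covers worsening of dental conditions (SAP 6.2.4.1), would carry a new finding into the AE tables.

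**The case against.** The strongest reply is that treatment-emergent soft-tissue change is already in the primary analysis. Such findings must be recorded as AEs, with severity and relatedness assessed and the same examiner following each subject. TREF13 to TREF16 tabulate AEs by system organ class, preferred term, severity and relationship in the Safety population, and AE incidence is the primary endpoint. The AE terms reported from the earlier trial (Protocol 5.5.2) often name the site, for example the tongue or gingiva. The listings LREF09 and LREF10 show each subject's result by visit, and with about 26 subjects they can be read by hand.

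Most of this stands. A reader might infer from the TREF17 layout that new or worsened local reactions could go unseen in the safety analysis as a whole. The documents do not support that, because the AE rule and the listings provide two other routes. Nor do they support a claim that the tables print percentages alone, since counts are printed too, or that hard-tissue findings are likely to be masked by resolution.

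What remains is narrower. The AE tables depend on each exam change having been entered as an AE, and no exam-based count is planned to check this. The LREF09 and LREF10 shells as printed have no treatment column, so reading them by hand is not a prespecified comparison between arms. The hard-tissue route to AEs is not stated.

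**Conclusion.** The point holds in a limited form and is minor. The exam tables planned in SAP 7.3 and TREF17 do not show within-subject change, although detecting change is the stated reason for recording soft-tissue abnormalities at baseline. The effect is confined to soft-tissue sites where some subjects are abnormal on Day 0. Its size depends on baseline rates that the documents do not give; under the assumed 2/13 at both visits, the uncertainty is 0 to 2 subjects in an arm. Exclusion of gross oral pathology (E09) may keep baseline abnormalities few, which would make the ambiguity smaller. The conclusion concerns the exam tables, their cross-check with AEs and the unstated hard-tissue rule. It does not reach the AE analysis itself.

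**What to change.** 1. In SAP 7.3 and the TREF17 shells, add a Day 0 to Day 4 shift count for each item and for any item, by treatment received in the Safety population: new since Day 0 (with the number normal or absent on Day 0 as denominator), resolved, and unchanged.
2. Take worsening of an existing abnormality from the AE record, since the exam field is binary and the listing shells carry no grade.
3. Reconcile new findings in LREF09 and LREF10 against the AE listing LREF16.
4. State whether new or worsened hard-tissue findings are recorded as AEs.

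While the shells are open, the soft-tissue column labels can be changed from Present/Absent to Normal/Abnormal to match how the exam is recorded. This is clerical and alters no count.

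The cost is a few extra table columns and minor programming. The shift counts use data already collected.
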